8.1.2 Leukapheresis Phase

A subject that meets all inclusion and none of the exclusion criteria will be eligible for leukapheresis. If the investigator believes a subject may require a second leukapheresis day for any reason, the medical monitor should be contacted for discussion and planning. Subjects in the leukapheresis phase of the study may receive bridging therapy under the direction of their physicians (see Section 6.1.3.2) and should undergo associated standard-of-care assessments.

Prior to entering the treatment phase, repeat BM assessment should be performed for Arm assignment if the assessment for study entry was prior to signing consent, > 6 weeks have passed since the screening BM assessment, or if warranted by change in clinical condition, or if subject has received bridging therapy other than hydroxyurea. If an Arm 1 subject is found to have $\geq 5\%$ bone marrow blasts at repeat BM assessment, the subject may be re-assigned to Arm 2 or, if Arm 2 is not yet enrolling subjects, the subject may receive NTLA-5001 at Dose Level -1.

8.1.3 Treatment Phase

After leukapheresis, subjects who meet criteria for treatment per Section 8.1.3.1 below and who have manufactured NTLA-5001 that meet release requirements will enter the treatment phase for the administration of lymphodepleting chemotherapy (Section 6.1.3.3) and study medication (Section 6.1.1). Individual subjects will participate in the treatment phase and follow-up phase for safety and efficacy assessments up to 112 weeks or until the subject is no longer receiving clinical benefit. Subjects who are no longer receiving clinical benefit will continue to be followed with clinic visits to safety every 12 weeks until 112 weeks after administration of NTLA-5001 (see SoA Section 1.3).

8.1.3.1 Criteria for Entering the Study Treatment Phase

Subjects must be reassessed for entry into the study treatment phase within 1 week of lymphodepleting chemotherapy.

Subjects must meet all of the following inclusion criteria:

1. Subject must have a projected life expectancy of at least 6 weeks.
2. Subject must have an ECOG performance status of 0 to 2.
3. Subjects must have adequate organ function defined as:
 - $AST \leq 2.5 \times ULN$ and $ALT \leq 2.5 \times ULN$ (unless considered due to leukemic organ involvement).
 - $Bilirubin \leq 1.5 \times ULN$ (unless considered due to leukemic organ involvement). Note: Subjects with Gilbert's Syndrome may have a bilirubin $> 1.5 \times ULN$ but must have direct bilirubin $\leq 1 \times ULN$.
 - $eGFR \geq 30$ mL/min; determined by CKD-Epi Study equation.

Subjects must not meet any of the following exclusion criteria:

1. Subjects with a history of allogeneic HCT are excluded if:

- Subjects have evidence of ongoing active GvHD, or
 - Subjects are on active immunosuppression for GvHD prophylaxis (must be off for 30 days prior to enrollment). Physiologic steroid replacement with ≤ 0.2 mg/kg/day methylprednisolone or equivalent is permitted.
2. Must not have signs or symptoms indicative of CNS involvement by tumor. A CNS evaluation should be performed to rule out CNS involvement if indicated by signs or symptoms.
 3. Must not have active DIC, bleeding or coagulopathy during screening.
 4. Must be eligible to receive lymphodepleting chemotherapy doses per protocol Section 6.1.3.3
 5. Must not have leukocytosis $\geq 20,000$ WBC/ μ L despite hydroxyurea or rapidly progressive disease (e.g., recent increase in blast count above 50%) that in the estimation of the investigator or Sponsor would compromise ability to complete study therapy.
 6. Must not have any condition, laboratory abnormality, or other reason that, in the investigator's opinion, could adversely affect the safety of the subject, impair the assessment of study results, or preclude compliance with the study.

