Study Arm assessment	X	X*																Study Arm assessment will be determined by the investigator. X*: Repeat assessment of Study Arm eligibility if repeat BM done.	
EORTC QLQ-C30	X																		
Study-required Procedures and Treatment																			
Leukapheresis		X																	Permitted if clinically indicated during the LP/cell manufacturing period. This bridging therapy may take place between leukapheresis and treatment. Any treatment required for bridging therapy will be collected on the concomitant medications CRF. See Section 6.1.3.2 for washout periods.
Bridging therapy (if clinically required)		X																	Assessment of eligibility to enter treatment phase should be performed within 1 week prior to Day -5 (see Section 8.1.3.1)
Meets entry and exclusion for treatment phase		X																	Lymphodepleting chemotherapy may be administered in the Inpatient or Outpatient setting. See Section 6.1.3.3
Lymphodepleting chemotherapy				X	X	X													Administer within 1 hour of NTLA-5001 dosing (see Section 6.1.3 for details).
Premedication								X											
NTLA-5001 dosing									X										
In unit observation								X	X	X	X	X	X	X	X	X	X*		X*: Only UK subjects are required to be hospitalized for days 8-14.

Note: All assessments on Day 0 are performed prior to infusion, unless otherwise indicated.

██████████ AML = acute myeloid leukemia; BM = bone marrow; CK = cell kinetics; CRF = case report form; ECOG = Eastern Cooperative Oncology Group; EORTC QLQ-C30 = European Organization for Research and Treatment of Cancer Quality of Life Questionnaire; LD = lymphodepletion; LP = leukapheresis; PBMC = peripheral blood mononuclear cell; PCR = polymerase chain reaction; RBC = red blood count; SCR = screening; SARS-CoV-2 = severe acute respiratory syndrome coronavirus 2

- a. The screening period will be up to 28 days prior to enrollment.
- b. In-patient observation on days 8-14 is required for UK subjects only.

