4.1.2 Screen Failures

Screen failures are defined as subjects who consent to participate in the clinical study but are not subsequently dosed with NTLA-5001.

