5 STUDY POPULATION

Eligibility criteria will be evaluated during the 28-day screening period. Before any study-specific activities/procedures, the appropriate written informed consent must be obtained (see Section 11.1.3). Prospective approval of protocol deviations to recruitment and enrollment criteria, also known as protocol waivers or exemptions, are not permitted.

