5.2 Exclusion Criteria

Subjects must not meet any of the following exclusion criteria:

1. Must not have received prior therapy as follows:
 - Chemotherapy or other targeted antileukemic therapy within 7 days of leukapheresis. Hydroxyurea is permitted up to 72 hours prior to leukapheresis.
 - Hematopoietic growth factors or other immunomodulatory therapy within 7 days of leukapheresis
 - Systemic steroids within 3 days of leukapheresis, except physiologic steroid replacement with ≤ 0.2 mg/kg/day methylprednisolone or equivalent
 - Prior therapy including investigational therapy targeted to WT1 such as vaccine therapy or cell therapy
 - Live vaccine 28 days or fewer prior to planned administration of lymphodepleting therapy
2. Subjects with a history of allogeneic HCT are excluded if:
 - Subjects are less than 84 days post-transplant, or
 - Subjects have evidence of ongoing active graft vs host disease (GvHD) requiring systemic immunosuppressants, or
 - Subjects have received donor lymphocyte infusion (DLI) within 28 days of leukapheresis, or
 - Subjects are on active immunosuppression for GvHD prophylaxis (must be off for 30 days prior to enrollment). Physiologic steroid replacement with ≤ 0.2 mg/kg/day methylprednisolone or equivalent is permitted.
3. [REDACTED]
4. Must not have signs or symptoms indicative of central nervous system (CNS) involvement by tumor. A CNS evaluation should be performed to rule out CNS involvement if indicated by signs or symptoms.
5. Must not have CNS co-morbidity such as transient ischemic attacks, cerebrovascular accident, seizure disorder, or other disorder that could confound neurotoxicity assessments.

6. Must not have severe autoimmunity that has required systemic steroid therapy or other immunomodulatory therapy.
7. Must not have active disseminated intravascular coagulation (DIC), bleeding or coagulopathy during screening.
8. Must be eligible to receive lymphodepleting chemotherapy doses per protocol Section 6.1.3.3
9. Must not have leukocytosis $\geq 20,000$ WBC/ μ L despite hydroxyurea or rapidly progressive disease (e.g., recent increase in blast count above 50%) that in the estimation of the investigator or Sponsor would compromise ability to complete study therapy.
10. Must have recovered from the acute side effects of their prior therapy, such that eligibility criteria are met.
11. Female subjects of childbearing potential are excluded:

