5.3 Criteria for Entering the Study Treatment Phase

After leukapheresis, subjects must meet criteria for treatment before lymphodepleting chemotherapy is administered. Criteria for entering the Study Treatment Phase are in Section [8.1.3.1](#).

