8.1 General Study Periods

8.1.1 Screening and Enrollment

Screening

The screening period will be up to 28 days, and a subject that meets all inclusion and none of the exclusion criteria will be enrolled and proceed to the leukapheresis phase in Arm 1 for subjects with AML blasts <5% of bone marrow or in Arm 2 for subjects with AML blasts \geq 5% of bone marrow.

All screening evaluations must be completed and reviewed to confirm that potential subjects meet all eligibility criteria. The investigator will maintain a screening log to record details of all subjects screened and to confirm eligibility or record reasons for screening failure, as applicable. Procedures conducted as part of the subject's routine clinical management (e.g., blood count) and obtained before signing of the informed consent form (ICF) may be utilized for screening or baseline purposes, provided the procedures met the protocol-specified criteria and were performed within the time frame defined in the SoA.

As outlined below, retesting during screening and rescreening is permitted.

Retesting During Screening

Retesting is defined as repeating laboratory tests within the same screening period.

If retesting goes beyond the 28-day screening period, the subject will be classified as a screen failure and will need to go through the rescreening process.

Rescreening

Subjects who fail to qualify for the study based on laboratory tests may be considered for rescreening at the discretion of the investigator if it is considered that the subject's status has changed, and the subject may now qualify for the study. Screening is limited to 2 attempts (initial screening and 1 additional rescreening attempt). A new informed consent is required to be signed prior to rescreening. See Section 11.1.3 for Informed Consent Process details.

Enrollment

The study population will be enrolled in 2 independent Arms.

Subjects in Arm 1 will have < 5.0% AML blasts in bone marrow on locally assessed morphology, and no evidence of blasts in peripheral blood or extramedullary disease (i.e., are in CR/CRi), and MRD identified at a frequency > 0.1% by the central laboratory, [REDACTED]

Subjects in Arm 2 will have $\geq 5.0\%$ AML blasts in BM by locally assessed morphology.

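### The treatment-phase exclusion for DIC, bleeding or coagulopathy is tied to the screening period, which has already closed when the criterion is applied

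*Protocol*

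**What the plan says.** Protocol Section 5.3 places a second eligibility gate between leukapheresis and chemotherapy: "After leukapheresis, subjects must meet criteria for treatment before lymphodepleting chemotherapy is administered". Section 8.1.3.1 holds the list and requires the check within 1 week of lymphodepletion. Table 1-1 puts it within 1 week before Day -5, in a Reassessment column headed Day -12 to -6.

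Exclusion 3 in that list is "Must not have active DIC, bleeding or coagulopathy during screening". Apart from spelling out the abbreviation, study-entry exclusion 7 in Section 5.2 has the same words: "Must not have active disseminated intravascular coagulation (DIC), bleeding or coagulopathy during screening".

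The protocol says when screening takes place:

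- Section 5: "Eligibility criteria will be evaluated during the 28-day screening period".
- Table 1-1, note a: "The screening period will be up to 28 days prior to enrollment".
- Section 8.1.1: "a subject that meets all inclusion and none of the exclusion criteria will be enrolled and proceed to the leukapheresis phase".

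**The concern.** The time anchor is right in Section 5.2, where the criterion is applied during screening. In Section 8.1.3.1 the same anchor points back to a period that is over. Taken literally, the item re-tests a question settled at enrollment and is silent on the subject's condition on the day of the recheck.

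This is the last written eligibility gate before chemotherapy and a first-in-human T cell product. The protocol itself names poor coagulation among the typical symptoms of AML (Section 2.3.2) and coagulopathy among the problems to be treated in severe CRS (Section 6.7.2). A condition that is a named exclusion at study entry would, at the gate closest to treatment, depend on exclusion 6, which turns on the investigator's opinion. Treating a subject with new DIC would not breach exclusion 3.

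**Working it through.** The plan states no figure on this point. The check sets the sections in time order and then sizes the gap from the protocol's own intervals.

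**Order of events**

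1. Screening, up to 28 days, before enrollment (Table 1-1 note a).
2. Enrollment, then leukapheresis (Section 8.1.1).
3. Manufacture and optional bridging (Section 6.1.3.2).
4. Reassessment under Section 8.1.3.1, Day -12 to Day -6.
5. Lymphodepletion, Day -5 to Day -3, and infusion on Day 0.

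The window named in exclusion 3 closes at step 2. The criterion is applied at step 4.

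**Comparison with the neighbouring items.** Exclusions 2 (CNS signs) and 5 (leukocytosis or rapid progression) also come from Section 5.2 but carry no screening anchor, so they work at the recheck. Other criteria were adapted for this gate: life expectancy goes from 12 to 6 weeks, and ECOG from 0–1 to 0–2. Exclusion 3 kept its entry-stage anchor. Exclusion 1 has a similar leftover in its reference to 30 days before enrollment, but that is minor, because active GvHD and current prophylaxis are excluded at the recheck anyway.

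**Uncovered time, bridged subjects.** Bridging follows leukapheresis, which follows enrollment, so the washout before Day -5 is a lower bound on the time from enrollment to Day -5. Day -12 is 7 days before Day -5, and Day -6 is 1 day before it.

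| Washout | Enrollment to Day -5 | Enrollment to recheck on Day -12 | Enrollment to recheck on Day -6 |
|---|---|---|---|
| 2 weeks | at least 14 days | at least 14 − 7 = 7 days | at least 14 − 1 = 13 days |
| 4 weeks | at least 28 days | at least 28 − 7 = 21 days | at least 28 − 1 = 27 days |

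**Uncovered time, from the marrow rule.** Section 8.1.2 asks for a repeat marrow if more than "6 weeks have passed since the screening BM assessment", that is, more than 42 days. Assume that the marrow was drawn within a screening period of at most 28 days:

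- Marrow on the first screening day: the trigger falls more than 42 − 28 = 14 days after enrollment.
- Marrow on the last screening day: the trigger falls more than 42 − 0 = 42 days after enrollment.

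Section 8.1.2 also uses the word screening for the earlier period, as distinct from the time just before treatment.

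**The case against.** The strongest reply is that no sensible site would read the item that way. The whole list is introduced as a reassessment close to chemotherapy, the item says active, and only a reading that makes it pointless looks back to a closed period. The protocol is also loose about where eligibility testing ends. Table 1-1 marks one eligibility row at screening and again at the recheck. Entry exclusion 11c allows a pregnancy test at Day 0. Section 4.1.2 defines screen failures as "subjects who consent to participate in the clinical study but are not subsequently dosed with NTLA-5001". This is good evidence of intent, and the intent was probably to test current status. None of it extends the screening period or changes what exclusion 3 says.

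A second reply is that a new coagulopathy would be caught anyway. Exclusion 6 is mandatory and has no screening anchor, and Section 8 asks for immediate safety concerns to be discussed with the sponsor. That backstop is real, but it rests on judgment. If it were enough, exclusions 2, 3 and 5 would not need to be listed separately. It is also fair that exclusion 3 gives no laboratory cutoff, so some judgment remains under any wording. The difference is between a named condition that must be absent and a general opinion.

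Two limits stand. The intervals show that time passes, not that anyone was wrongly treated. The SAP (Section 7) records that the sponsor terminated the study when only 2 subjects had received the product, so the practical value now lies in correcting the text and in any reuse of it.

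**Conclusion.** The concern holds. As written, one of the six treatment-phase exclusions covers none of the time after enrollment. That time is at least 7 to 13 days to the recheck after a 2-week-washout bridging agent and at least 21 to 27 days after a 4-week agent. Apart from bridging, the marrow rule foresees reaching a point more than 14 to more than 42 days after enrollment.

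The conclusion rests on reading screening as Table 1-1 note a and Section 8.1.1 define it. The marrow figures also assume that the sample was taken within screening. No sample size, endpoint or analysis is affected. How often DIC, bleeding or coagulopathy begins in this interval is not given in the documents, so no harm is quantified.

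**What to change.** In Section 8.1.3.1, exclusion 3, replace the closing reference to screening with *at the treatment-phase reassessment*. Leave Section 5.2 exclusion 7 as it is. No change to any washout is needed.

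The cost is one phrase of protocol wording. Some subjects may be delayed or excluded at the recheck, at a rate the documents do not give. Table 13-1 includes a coagulation panel, but its row in the schedule is not in the available text. The sponsor should therefore confirm that a panel is drawn at the reassessment.

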8.1.4 End of Study Visit

A subject will have an End of Study visit at Week 112 or at the time the subject is discontinued from efficacy assessments by the investigator because the subject is no longer receiving clinical benefit. Subjects who are no longer receiving clinical benefit will continue to be followed with clinic visits (focused physical exam, vital signs, weight, and assessment for treatment-related AEs and treatment-related serious adverse events [SAEs]) every 12 weeks until 112 weeks after administration of NTLA-5001. Subjects who are not receiving clinical benefit may receive additional treatment or supportive care per their Investigators for the duration of the study.

8.1.5 Long-term Follow up

Following participation in the study, all subjects who have received study medication in this study will undergo long-term safety monitoring in order to comply with local regulatory requirements/guidance for subjects administered a gene therapy. All subjects will be followed for a minimum of 5 years in the UK and for a minimum of 15 years in the US. Additional details on the long-term follow-up will be provided outside of this clinical study and will be in place before the first subject completes their Week 112 study visit.

8.2 General Assessments

8.2.1 Demographics

Demographic data collection including sex, age, race, and ethnicity will be collected in order to study their possible association with subject safety and treatment effectiveness. Additionally, demographic data will be used to study the impact on biomarker variability and CK of the protocol-required therapies.

8.2.2 Medical History

The investigator or designee will collect a complete medical and surgical history that started within 3 years prior to screening through time of signing of informed consent. Medical history will include information on the subject's concurrent medical conditions. Record all findings on the medical history CRF.

8.3 Efficacy Assessments

8.3.1 Bone Marrow Sampling and Disease Assessment

Bone marrow aspirate and biopsy will be performed until the subject achieves complete remission and has no evidence of MRD. Thereafter, subjects should undergo bone marrow aspirates every 12 weeks for 1 year after remission is first documented. Subsequently, subjects in CR are not required to have additional bone marrow aspirations unless clinically indicated. Bone marrow will be used for hematological assessment, and local cytomorphological assessment will be performed. From each sample, mandatory evaluation of MRD by difference from normal flow cytometry will also be conducted via central laboratory analysis. The following samples will be obtained for local cytomorphological assessment and MRD measurement at the central laboratory (listed in recommended priority order):

- local cytomorphology: bone marrow smears (slides)
- MRD: aliquots for difference from normal flow cytometry
- evaluation of immune parameters and NTLA-5001 cells

For cytomorphology, if a marrow aspiration is not possible, or the aspirate does not contain any bone marrow, a core biopsy will be done. In case of core biopsies, no central MRD assessment will be possible.

8.3.2 EORTC QLQ-C30

The EORTC QLQ-C30 was developed to assess the quality of life in cancer subjects across tumor types. It is a self-reporting 30-item generic instrument which assesses 15 domains consisting of 5 functional domains (physical, role, emotional, cognitive, social), 9 symptom scales (fatigue, nausea and vomiting, pain, dyspnea, insomnia, appetite loss, constipation, diarrhea, financial difficulties), and a global health status/quality of life scale (Aronson et al, 1993). The recall period is the past week. The QLQ-C30 will take approximately 9 minutes to complete.

8.4 Safety Assessments

Planned time points for all safety assessments are provided in the SoA (Section 1.3).

8.4.1 Vital Signs

Vital signs, including systolic and diastolic blood pressures (mm Hg), pulse rate (beats/minute) and temperature will be obtained and recorded. All vital sign measures will be obtained with the subject in the sitting or supine position.

If clinically significant worsening of a finding from screening is noted at any study visit, the abnormality will be documented as an AE on the AE page of the eCRF as defined in Adverse Events (Section 8.5.1).

8.4.2 Physical Examination

Standard, full physical examinations will be performed to assess weight, height, general appearance, skin, eyes, ears, nose, throat, neck, cardiovascular, chest and lungs, abdomen, musculoskeletal, neurologic, lymphatic system, reproductive system, and mental status. Genitourinary and rectal system exams are to be performed only if clinically indicated. Focused physical examinations should be symptom directed and consider potential sites of on target / off tumor toxicity. The PI will inquire if the subject has experienced testicular/scrotal pain, swelling, and erythema for males and lower abdominal pain or vaginal bleeding for women, or any reproductive symptoms, whether the subject is trying to conceive, or has successfully conceived. Should a pregnancy occur a detailed in-utero assessment will be performed. Physical exam at each clinic visit will assess for any new pleural or peritoneal effusions.

If clinically significant worsening of findings from baseline is noted at any study visit, the change will be documented as an AE on the AE page of the case report form (CRF). Clinical significance is defined as any variation in physical findings, which has medical relevance that could result in an alteration in medical care (see Section 8.5.1). The investigator will continue to monitor the subject until the investigator determines that the findings are no longer clinically significant.

Note: Any finding assessed by the investigator to be associated with the underlying AML, unless judged by the investigator to be more severe than expected for the subject's condition, will not be reported as an AE.

